Injection Site Pain (pain without touching) Or Tenderness (pain when area is touched)	Pain/tenderness causing no or minimal limitation of use of limb	Pain/tenderness limiting use of limb OR Pain/tenderness causing greater than minimal interference with usual social & functional activities	Pain/tenderness causing inability to perform usual social & functional activities	Pain/tenderness causing inability to perform basic self-care function OR Hospitalization (other than ER visit) indicated for management of pain/tenderness
Injection Site Reaction (Localized), > 15 Years Pediatric ≤ 15 Years	Erythema OR Induration of 5 × 5 cm to 9 × 9 cm (or 25–81 × cm ²) Erythema OR Induration OR Edema present but ≤ 2.5 cm diameter	Erythema OR Induration OR Edema > 9 cm any diameter (or > 81 cm ²) Erythema OR Induration OR Edema > 2.5 cm diameter but < 50% surface area of the extremity segment (eg, upper arm/thigh)	Ulceration OR Secondary infection OR Phlebitis OR Sterile abscess OR Drainage Erythema OR Induration OR Edema involving ≥ 50% surface area of the extremity segment (eg, upper arm/thigh) OR Ulceration OR Secondary infection OR Phlebitis OR Sterile abscess OR Drainage	Necrosis (involving dermis and deeper tissue) Necrosis (involving dermis and deeper tissue)
Pruritis Associated with Injection See also Skin: Pruritis (itching—no skin lesions)	Itching localized to injection site AND Relieved spontaneously or with < 48 h treatment	Itching beyond the injection site but not generalized OR Itching localized to injection site requiring ≥ 48 h treatment	Generalized itching causing inability to perform usual social & functional activities	NA

ENDOCRINE/METABOLIC				
	Grade 1	Grade 2	Grade 3	Grade 4
Lipodystrophy (eg, back of neck, breasts, abdomen)	Detectable by study participant or caregiver (for young children and disabled adults)	Detectable on physical exam by health care provider	Disfiguring OR Obvious changes on casual visual inspection	NA
Diabetes Mellitus	NA	New onset without need to initiate medication OR Modification of current meds to regain glucose control	New onset with initiation of indicated med OR Diabetes uncontrolled despite treatment modification	Life-threatening consequences (eg, ketoacidosis, hyperosmolar non-ketotic coma)
Gynecomastia	Detectable by study participant or caregiver (for young children and disabled adults)	Detectable on physical exam by health care provider	Disfiguring OR Obvious on casual visual inspection	NA
Hyperthyroidism	Asymptomatic	Symptomatic causing greater than minimal interference with usual social & functional activities OR Thyroid suppression therapy indicated	Symptoms causing inability to perform usual social & functional activities OR Uncontrolled despite treatment modification	Life-threatening consequences (eg, thyroid storm)
Hypothyroidism	Asymptomatic	Symptomatic causing greater than minimal interference with usual social & functional activities OR Thyroid replacement therapy indicated	Symptoms causing inability to perform usual social & functional activities OR Uncontrolled despite treatment modification	Life-threatening consequences (eg, myxedema coma)
Lipoatrophy (eg, fat loss from the face, extremities, buttocks)	Detectable by study participant or caregiver (for young children and disabled adults)	Detectable on physical exam by health care provider	Disfiguring OR Obvious on casual visual inspection	NA

GENITOURINARY				
	Grade 1	Grade 2	Grade 3	Grade 4
Intermenstrual Bleeding (IMB)	Spotting observed by participant OR Minimal blood observed during clinical or colposcopic exam	Intermenstrual bleeding not greater in duration or amount than usual menstrual cycle	Intermenstrual bleeding greater in duration or amount than usual menstrual cycle	Hemorrhage with life-threatening hypotension OR Operative intervention indicated
Urinary Tract obstruction (eg, stone)	NA	Signs or symptoms of urinary tract obstruction without hydronephrosis or renal dysfunction	Signs or symptoms of urinary tract obstruction with hydronephrosis or renal dysfunction	Obstruction causing life-threatening consequences

INFECTION				
	Grade 1	Grade 2	Grade 3	Grade 4
Infection (any other than HIV infection)	Localized, no systemic antiꞑbial treatment indicated AND Symptoms causing no or minimal interference with usual social & functional activities	Systemic antiꞑbial treatment indicated OR Symptoms causing greater than minimal interference with usual social & functional activities	Systemic antiꞑbial treatment indicated AND Symptoms causing inability to perform usual social & functional activities OR Operative intervention (other than simple incision and drainage) indicated	Life-threatening consequences (eg, septic shock)

Basic Self-care Functions: Activities such as bathing, dressing, toileting, transfer/movement, continence, and feeding.

Usual Social & Functional Activities: Adaptive tasks and desirable activities, such as going to work, shopping, cooking, use of transportation, pursuing a hobby, etc

Appendix 5. Pregnancy Precautions, Definition for Female of Childbearing Potential, and Contraceptive Requirements

1) Pregnancy and Contraception Requirements for Males and Females of Childbearing Potential

Pregnancy must be excluded before the start of treatment with study drug and prevented thereafter by reliable contraceptive methods. A urine or serum pregnancy test will be performed for all females of childbearing potential at the screening visit and at each dosing visit (Visits 2, 4, 6, 7, and 8) prior to administration of study drug to ensure pregnant women are not included or treated with study drug in the trial. Please refer to the latest version of the Investigator's Brochure for additional information about the effects of presatovir.

2) Definition of Female of Childbearing Potential

For the purposes of this study, a female subject of childbearing potential is a nonmenopausal female who has not had a hysterectomy, bilateral oophorectomy, or medically documented ovarian failure. This definition includes a pubertal female who has not yet started menstruating. A woman who has had a tubal sterilization is considered to be of childbearing potential.

A female subject may be considered menopausal in either of the following conditions:

- Surgical menopause: Appropriate medical documentation of prior complete bilateral oophorectomy (ie, surgical removal of the ovaries and occurring at the age at which the procedure was performed)
- Spontaneous menopause: Permanent cessation of previously occurring menses as a result of ovarian failure with documentation of hormonal deficiency by a certified health care provider. The worldwide mean age of spontaneous menopause is 49.24 (SD 1.73) years
- A hormonal deficiency should be properly documented in the case of suspected spontaneous menopause as follows:
 - If age ≥ 54 years and with the absence of normal menses: serum follicle stimulating hormone (FSH) level elevated to within the postmenopausal range based on the laboratory reference range where the hormonal assay is performed
 - If age < 54 years and with the absence of normal menses: negative serum or urine human chorionic gonadotropin (hCG) with concurrently elevated serum FSH level in the postmenopausal range, depressed estradiol (E2) level in the postmenopausal range, and absent serum progesterone level, based on the laboratory reference ranges where the hormonal assays are performed

3) Contraceptive Requirements

Female subjects of childbearing potential and male subjects must agree to either continue abstinence from sexual intercourse or utilize protocol specified methods of contraception if they choose to engage in intercourse from the screening/enrollment visit throughout the study period

and for 30 days following the last dose of study drug (90 days for males). Female study subjects of childbearing potential will undergo regular pregnancy testing while taking presatovir. The investigator will counsel subjects on the protocol specified method(s) for avoiding pregnancy in case the subject chooses to engage in heterosexual intercourse.

Protocol specified contraceptive methods are as follows: (1) a combination of one hormonal method and one barrier method; or (2) use of an intrauterine device (IUD) or tubal sterilization; see [Appendix Table 1](#) below. Acceptable hormonal methods include injectable progesterone, progesterone implants, combination oral contraceptives, transdermal contraceptive patch, and vaginal ring. Acceptable barrier methods include diaphragm with spermicide, cervical cap with spermicide, and the male condom with spermicide. Female subjects must use either a hormonal method or a barrier method if the partner has a vasectomy and the male partner should be the sole partner for that subject. For a vasectomy, appropriate post-vasectomy documentation of the absence of sperm in the ejaculate must be available. If a subject has undergone tubal sterilization or has had a Copper T 380A IUD or LNG 20 IUD inserted, no other contraception is needed.

If tubal sterilization is via the Essure procedure, verification of tubal blockage by hysterosalpingogram (HSP) must be performed approximately 3 months after microinsertion. Prior to verification, Essure is not considered a reliable form of contraception and the contraception methods described below must be used. Female subjects who utilize hormonal contraceptives as one of their birth control methods must have used the same method for at least 3 months before study dosing.

Female subjects of childbearing potential must have a negative urine or serum pregnancy test at screening and at each dosing visit (Visits 2, 4, 6, 7, and 8) prior to receiving study drug.

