5.4. Prior and Concomitant Medications

Strong and moderate inducers of CYP enzymes may reduce the exposure of presatovir. Preliminary PK results from a clinical drug-drug-interaction (DDI) study (GS-US-218-1409) demonstrated that induction of CYP enzymes with rifampin or efavirenz resulted in an 82% or 56% decrease, respectively, in presatovir AUC_{inf}. Therefore, concomitant administration of strong or moderate CYP inducers {FDA 2012} (including but not limited to rifampin, St John's Wort, carbamazepine, phenytoin, efavirenz, bosentan, etravirine, modafinil, and nafcillin) is excluded to avoid potential drug resistance.

Cyclosporine, a weak CYP3A inhibitor and a potent inhibitor of efflux transporters (P glycoprotein [P-gp], breast cancer resistant protein [BCRP]) and the hepatic uptake organic anion transporter proteins (OATP1B1 and OATP1B3), has been associated with a mild increase in presatovir plasma exposure (10.6% increase in C_{max} and 26.1% increase in AUC_{inf}). Thus presatovir can be coadministered with inhibitors of P-gp, BCRP, OATP 1B1, or OTAP1B3 without dose modification.

The effect of co-administration with strong and moderate CYP3A inhibitors on presatovir PK is currently being investigated in a clinical drug-drug interaction study.

Presatovir is not expected to significantly alter the PK of concomitant medications that are substrates of major human CYP enzymes or drug transporters. Presatovir is not expected to be an inhibitor of common human CYP enzymes (CYP1A2, CYP2B6, CYP2C8, CYP2C9, CYP2C19, CYP3A, and CYP2D6), human UGT1A1, or major drug transporters (OATP1B1/1B3, BCRP, P-gp, OCT1, OCT2, BSEP, OAT1, and OAT3) at clinically relevant concentrations. Presatovir is also not an inducer through AhR or PXR at concentrations up to 50 µM.

Presatovir may cause concentration-dependent inhibition of multidrug and toxin extrusion via transporters MATE1 and MATE2-K with IC₅₀ values of 0.50 and 3.8 µM, respectively. When co-administered with renally eliminated concomitant medications (ie, filtration plus secretion), presatovir may increase the exposures of substrates secreted by the MATEs transporters, such as ganciclovir, acyclovir, levofloxacin, metformin, captopril, procainamide, fexofenadine, cimetidine, cephadrine, and cephalixin. Dosing and safety monitoring should be consistent with prescribing information, in particular for agents which require dose reductions in the setting of renal impairment.

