8.6.3. Laboratory Evaluations

Selected laboratory data will be summarized using only observed data. Data and change from Baseline at all scheduled time points will be summarized.

Graded laboratory abnormalities will be defined using the grading scheme in [Appendix 4](#). Grading of laboratory abnormalities for analysis purposes will be performed by GSI.

Incidence of treatment-emergent laboratory abnormalities, defined as values that increase at least 1 toxicity grade from Baseline at any time post Baseline up to and including Day 28 will be summarized by treatment group. If Baseline data are missing, then any graded abnormality (ie, at least a Grade 1) will be considered treatment emergent.

Laboratory abnormalities that occur before the first dose of IMP or after the subject has been discontinued from treatment for at least 28 days will be included in a data listing.

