Hyperuricemia	>ULN to 10.0 mg/dL >ULN to 597 μmol/L	> 10.0 to 12.0 mg/dL > 597 to 716 μmol/L	> 12.0 to 15.0 mg/dL > 716 to 895 μmol/L	> 15.0 mg/dL > 895 μmol/L
Hypouricemia	1.5 mg/dL to < LLN 87 μmol/L to < LLN	1.0 to < 1.5 mg/dL 57 to < 87 μmol/L	0.5 to < 1.0 mg/dL 27 to < 57 μmol/L	< 0.5 mg/dL < 27 μmol/L
Creatinine	> 1.50 to 2.00 mg/dL > 133 to 177 μmol/L	> 2.00 to 3.00 mg/dL > 177 to 265 μmol/L	> 3.00 to 6.00 mg/dL > 265 to 530 μmol/L	> 6.00 mg/dL > 530 μmol/L
Bicarbonate	16.0 mEq/L to < LLN 16.0 mmol/L to < LLN	11.0 to < 16.0 mEq/L 11.0 to < 16.0 mmol/L	8.0 to < 11.0 mEq/L 8.0 to < 11.0 mmol/L	< 8.0 mEq/L < 8.0 mmol/L
Triglycerides (Fasting)	NA	500 to 750 mg/dL 5.64–8.47 mmol/L	> 750 to 1200 mg/dL > 8.47–13.55 mmol/L	> 1200 mg/dL > 13.55 mmol/L

CHEMISTRY				
	Grade 1	Grade 2	Grade 3	Grade 4
LDL (Fasting)	130 to 160 mg/dL 3.35 to 4.15 mmol/L	>160 to 190 mg/dL >4.15 to 4.92 mmol/L	> 190 mg/dL >4.92 mmol/L	NA
Pediatric >2 to <18 years	110 to 130 mg/dL 2.84 to 3.37 mmol/L	>130 to 190 mg/dL >3.37 to 4.92 mmol/L	> 190 mg/dL >4.92 mmol/L	NA
Hypercholesterolemia (Fasting)	200 to 239 mg/dL 5.16 to 6.19 mmol/L	> 239 to 300 mg/dL > 6.19 to 7.77 mmol/L	> 300 mg/dL > 7.77 mmol/L	NA
Pediatric < 18 Years	170 to 199 mg/dL 4.39 to 5.15 mmol/L	> 199 to 300 mg/dL > 5.15 to 7.77 mmol/L	> 300 mg/dL > 7.77 mmol/L	NA
Creatine Kinase	3.0 to < 6.0 × ULN	6.0 to < 10.0 × ULN	10.0 to < 20.0 × ULN	≥ 20.0 × ULN

*Calcium should be corrected for albumin if albumin is < 4.0 g/dL

ENZYMES				
	Grade 1	Grade 2	Grade 3	Grade 4
AST (SGOT)	1.25 to 2.50 × ULN	> 2.50 to 5.00 × ULN	> 5.00 to 10.00 × ULN	> 10.00 × ULN
ALT (SGPT)	1.25 to 2.50 × ULN	> 2.50 to 5.00 × ULN	> 5.00 to 10.00 × ULN	> 10.00 × ULN
GGT	1.25 to 2.50 × ULN	> 2.50 to 5.00 × ULN	> 5.00 to 10.00 × ULN	> 10.00 × ULN
Alkaline Phosphatase	1.25 to 2.50 × ULN	> 2.50 to 5.00 × ULN	> 5.00 to 10.00 × ULN	> 10.00 × ULN
Total Amylase	> 1.0 to 1.5 × ULN	> 1.5 to 2.0 × ULN	> 2.0 to 5.0 × ULN	> 5.0 × ULN
Pancreatic Amylase	> 1.0 to 1.5 × ULN	> 1.5 to 2.0 × ULN	> 2.0 to 5.0 × ULN	> 5.0 × ULN
Lipase	> 1.0 to 1.5 × ULN	> 1.5 to 3.0 × ULN	> 3.0 to 5.0 × ULN	> 5.0 × ULN
Albumin	3.0 g/dL to < LLN 30 g/L to < LLN	2.0 to < 3.0 g/dL 20 to < 30 g/L	< 2.0 g/dL < 20 g/L	NA

URINALYSIS				
	Grade 1	Grade 2	Grade 3	Grade 4
Hematuria (Dipstick)	1+	2+	3-4+	NA
Hematuria (Quantitative) See Note below				
Females	>ULN - 10 RBC/HPF	> 10-75 RBC/HPF	> 75 RBC/HPF	NA
Males	6-10 RBC/HPF	> 10-75 RBC/HPF	> 75 RBC/HPF	NA
Proteinuria (Dipstick)	1+	2-3+	4+	NA

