Proteinuria, 24 Hour Collection				
Adult and Pediatric ≥ 10 Years	200 to 999 mg/24 h	>999 to 1999 mg/24 h	>1999 to 3500 mg/24 h	> 3500 mg/24 h
Pediatric > 3 Mo to < 10 Years	201 to 499 mg/m ² /24 h	>499 to 799 mg/m ² /24 h	>799 to 1000 mg/m ² /24 h	> 1000 mg/ m ² /24 h
Glycosuria (Dipstick)	1+	2-3+	4+	NA

Notes:

Toxicity grades for Quantitative and Dipstick Hematuria will be assigned by Covance Laboratory, however for other laboratories, toxicity grades will only be assigned to Dipstick Hematuria.

With the exception of lipid tests, any graded laboratory test with a result that is between the LLN and ULN should be assigned Grade 0.

If the severity of a clinical AE could fall under either one of two grades (e.g., the severity of an AE could be either Grade 2 or Grade 3), select the higher of the two grades for the AE.

CARDIOVASCULAR				
	Grade 1	Grade 2	Grade 3	Grade 4
Cardiac Arrhythmia (general) (By ECG or physical exam)	Asymptomatic AND No intervention indicated	Asymptomatic AND Non-urgent medical intervention indicated	Symptomatic, non-life-threatening AND Non-urgent medical intervention indicated	Life-threatening arrhythmia OR Urgent intervention indicated
Cardiac-ischemia/Infarction	NA	NA	Symptomatic ischemia (stable angina) OR Testing consistent with ischemia	Unstable angina OR Acute myocardial infarction
Hemorrhage (significant acute blood loss)	NA	Symptomatic AND No transfusion indicated	Symptomatic AND Transfusion of ≤ 2 units packed RBCs (for children ≤ 10 cc/kg) indicated	Life-threatening hypotension OR Transfusion of > 2 units packed RBCs indicated (for children ≤ 10 cc/kg) indicated
Hypertension (with repeat testing at same visit)	140–159 mmHg systolic OR 90–99 mmHg diastolic	> 159–179 mmHg systolic OR > 99–109 mmHg diastolic	> 179 mmHg systolic OR > 109 mmHg diastolic	Life-threatening consequences (eg, malignant hypertension) OR Hospitalization (other than ER visit) indicated
Pediatric ≤ 17 Years (with repeat testing at same visit)	NA	91st–94th percentile adjusted for age, height, and gender (systolic and/or diastolic)	≥ 95th percentile adjusted for age, height, and gender (systolic and/or diastolic)	Life-threatening consequences (eg, malignant hypertension) OR Hospitalization indicated (other than emergency room visit)
Hypotension	NA	Symptomatic, corrected with oral fluid replacement	Symptomatic, IV fluids indicated	Shock requiring use of vasopressors or mechanical assistance to maintain blood pressure

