7.2.2. Graded Laboratory Values

The criteria specified in the study protocol will be used to grade laboratory results as Grade 0, mild (Grade 1), moderate (Grade 2), severe (Grade 3), or potentially life threatening (Grade 4). Grade 0 includes all values that do not meet criteria for an abnormality of at least Grade 1. Some laboratory tests have criteria for both increased and decreased levels; analyses for each direction (ie, increased, decreased) will be presented separately.

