7.2.2.1. Treatment-Emergent Laboratory Abnormalities

Treatment-emergent laboratory abnormalities are defined as values that increase at least 1 toxicity grade from baseline at any post baseline time point, up to and including Day 28 visit. If the relevant baseline laboratory value is missing, then any abnormality of at least Grade 1 observed within the time frame specified above will be considered treatment emergent.

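### Creatinine is graded on absolute cut-offs only, and no planned table counts subjects by the rise from their own baseline; one descriptive table would close the gap

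*Protocol*

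**What the plan says.** **Grading.** In the chemistry part of protocol Appendix 4, creatinine Grade 1 is "> 1.50 to 2.00 mg/dL > 133 to 177" µmol/L, Grade 2 is "> 2.00 to 3.00 mg/dL > 177 to 265" µmol/L, Grade 3 is "> 3.00 to 6.00 mg/dL > 265 to 530" µmol/L, and Grade 4 lies above 6.00 mg/dL. The row has no criterion relative to baseline. The hemoglobin row (HIV negative) and the QTc row of the same appendix do have one. A note to the laboratory tables adds that, lipids apart, "any graded laboratory test with a result that is between the LLN and ULN should be assigned Grade 0".

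**Use in the analysis.** Protocol Section 8.6.3 ties the analysis to this scale: "Graded laboratory abnormalities will be defined using the grading scheme in" Appendix 4. SAP Section 7.2.2 says "Grade 0 includes all values that do not meet criteria for an abnormality of at least Grade 1", and SAP Section 7.2.2.1 says "Treatment-emergent laboratory abnormalities are defined as values that increase at least 1 toxicity grade from baseline at any post baseline time point", through the Day 28 visit. A marked abnormality (SAP 7.2.2.2) needs a rise of at least three grades.

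**Other creatinine outputs.** SAP 7.2.1 and Tables 15.11.6.2.6 and 15.11.6.2.7 give descriptive statistics by arm and visit for creatinine and creatinine clearance, including the minimum and maximum of the change from baseline. Table 15.11.6.2.9 covers the timed samples of the PK subgroup. SAP 7.2 provides by-subject listings.

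**Why kidney function has attention here.** Protocol Section 5.4 describes inhibition of the renal transporters MATE1 and MATE2-K and warns that "presatovir may increase the exposures of substrates secreted by the MATEs transporters", naming ganciclovir and acyclovir among them. Subjects are excluded only below a clearance of 30 mL/min (Section 4.3). Section 6.11.6 adds a creatinine sample 2 hours post-dose on Days 1 and 9 in the PK subgroup.

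**The concern.** A grade built on absolute concentration asks whether a subject has crossed 1.50 mg/dL, not how far that subject has moved. In subjects who start low, a large proportional loss of clearance can occur below the first cut-off and enter the incidence table as no abnormality. In subjects who start just under the cut-off, a small change is counted.

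The incidence table is where a reader will look for the number of subjects per arm whose creatinine rose. If large relative rises differ between arms but mostly end at or below 1.50 mg/dL, that table will not show it, and the plan has no other count that would.

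**Working it through.** The documents state no figure on this point, so there is nothing to reproduce. The check applies the written rules to example values. The creatinine values, and the subject in step 3, are assumptions.

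**1. Grade before and after.** Inputs: the Appendix 4 bands and the one-grade rule of SAP 7.2.2.1.

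| Baseline to later value (mg/dL) | Change | Grades | Counted as treatment-emergent |
|---|---|---|---|
| 0.50 to 1.00 | +100% | 0 to 0 | no |
| 0.60 to 1.20 | +100% | 0 to 0 | no |
| 0.75 to 1.50 | +100% | 0 to 0 | no |
| 0.76 to 1.52 | +100% | 0 to 1 | yes* |
| 0.50 to 1.50 | +200% | 0 to 0 | no |
| 0.60 to 1.50 | +150% | 0 to 0 | no |
| 1.45 to 1.55 | +6.9% | 0 to 1 | yes* |
| 1.50 to 1.51 | +0.7% | 0 to 1 | yes* |

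*Only if the later value exceeds the laboratory's upper limit of normal (ULN), because in-range results are set to Grade 0. The documents give no creatinine ULN.

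**2. Rise that can occur without leaving Grade 0.** Largest fold-rise = 1.50 / baseline: 3.0 from 0.5 mg/dL, 2.5 from 0.6, 2.0 from 0.75, 1.5 from 1.0 and 1.07 from 1.4. A doubling is missed exactly when the baseline is at most 1.50 / 2 = 0.75 mg/dL. An in-range rule with a ULN above 1.50 would only raise these figures.

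**3. What that means for clearance.** Cockcroft-Gault for an assumed woman of 60 years and 60 kg:

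- at 0.6 mg/dL: (140 − 60) × 60 × 0.85 / (72 × 0.6) = 4080 / 43.2 = 94.4 mL/min
- at 1.5 mg/dL: 4080 / (72 × 1.5) = 4080 / 108 = 37.8 mL/min

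That is a 60% fall, at Grade 0 throughout.

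**4. Illustration only.** Suppose baseline creatinine is lognormal with median 0.65 to 0.95 mg/dL and log-SD *s* of 0.25 to 0.35; neither range is in the documents. The share of *f*-fold rises that end at or below 1.50 mg/dL is Φ((ln(1.5/*f*) − ln(median)) / *s*).

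- *f* = 2: 0.72 (median 0.65, *s* 0.25) down to 0.17 (median 0.95, *s* 0.25)
- *f* = 1.5: 0.96 (median 0.65, *s* 0.25) down to 0.56 (median 0.95, *s* 0.35)

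**5. Whether another planned output supplies the count.**

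- *By-visit statistics.* A maximum change identifies at most one value per arm and visit, and it is not a ratio: +0.6 mg/dL may be 0.6 to 1.2 (+100%) or 1.4 to 2.0 (0.6/1.4 = +43%). Unscheduled visits are left out of these tables (SAP 3.8.3), and no worst post-baseline creatinine is summarised.
- *Listings.* The general listing flags out-of-range or graded values, so a doubling within range carries no flag. The abnormality listing of SAP 7.2.2.3 is triggered only by Grade 3 or 4 or by a marked abnormality. From Grade 0, marked means above 3.00 mg/dL, more than 5-fold from 0.6.
- *Adverse event tables.* Under protocol Sections 7.1.3 and 7.5, laboratory changes usually do not become adverse events unless they need intervention, affect dosing or come with symptoms.

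**The case against.** The other side has a good case. This is the sponsor's standard, versioned scale. Platelets, neutrophils, BUN, ALT, AST and bilirubin have no baseline-relative criterion either, so creatinine is not an oddity. The row follows a pre-specified rule, applied alike in both arms of a blinded trial. Kidney injury that is symptomatic, needs intervention or stops dosing would be recorded and counted as an adverse event, and its severity need not match the laboratory grade. An above-range creatinine at Grade 0 is still flagged in the listing. A fall from 94 to 38 mL/min would register in the clearance summaries. BUN is graded separately, timed creatinine has its own table, and the DMC reviews all safety data. Protocol Section 5.4 speaks of raised exposure to co-medications, not of kidney toxicity from presatovir.

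All of that stands, and it limits the point. A reader might infer that the plan's renal safety table miscounts in both directions. The documents do not support this: no table has that role, and the graded row counts what its definition says. A reader might also infer that the graded table is the only subject-level count of creatinine problems. The adverse event tables are a second, partial one.

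The objection does not supply the missing count. None of the outputs it names gives, by arm, the number of subjects with a large rise from their own baseline. The SAP also accepts elsewhere that grades may need a supplement: Section 7.2.3 adds subject counts at liver thresholds that are not Appendix 4 grades.

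**Conclusion.** The point holds as a cheap improvement to the renal safety assessment. The graded creatinine row is insensitive to relative rises, and no other planned output counts them by arm. The fold thresholds follow from the 1.50 mg/dL cut-off without further assumption. The small-rise example needs a baseline just under the cut-off and a ULN below the later value.

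The number of subjects affected is unknown. The ranges of 17–72% (doublings) and 56–96% (1.5-fold rises) are shares of hypothetical rises under assumed baselines. They illustrate the mechanism and are not estimates for this trial. It is also tempting to call small rises near 1.50 mg/dL harmless; the documents give no basis for that, and the point does not need it. Laboratory data are summarised descriptively only, and no efficacy, alpha or sample-size figure changes.

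**What to change.** In SAP Section 7.2.2, or beside Section 7.2.3, add one descriptive table by arm for the Safety Analysis Set with the number and percentage of subjects whose

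- highest post-baseline creatinine through Day 28 is at least 1.5, 2 and 3 times their own baseline;
- calculated clearance falls by at least 25% and 50% from baseline.

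Use the baseline definition of SAP 7.2.1, and take as denominator the subjects with a baseline and at least one post-baseline value. State whether unscheduled results count; including them matches the any-time-point rule of SAP 7.2.2.1. Keep the timed 2-hour samples in Table 15.11.6.2.9, so that PK-subgroup subjects do not get extra chances at a maximum. At constant age and weight the clearance fall is 1 − 1/fold, so a 50% fall equals a doubling and a 25% fall equals a 1.33-fold rise. The two sets of counts will overlap, and a footnote should say so.

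Leave the Appendix 4 grades, adverse event severity and subject management unchanged.

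The cost is a few lines of text and one more descriptive table. Creatinine and weight are already collected on Days 1, 5, 9, 13, 17, 22 and 28, and clearance is already tabulated. If the SAP is final, its introduction provides for recording the addition in the clinical study report.
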